Table 1 **Expected Mean Ratios and Coefficients of Variation for CHTP 1.2/CC after 5 Days or 90 Days of exposure**

Timepoint of assessment	Primary endpoint	CHTP 1.2/CC MR (CV)
Day 5	COHb	0.40 (0.32)
Day 5	3-HPMA	0.30 (0.50)
Day 5	MHBMA	0.15 (0.70)
Day 5	S-PMA	0.20 (0.70)
Day 90	Total NNAL	0.30 (0.60)

Abbreviations: 3-HPMA = 3-hydroxypropylmercapturic acid; CC = Combustible cigarettes; COHb = Carboxyhemoglobin; CV = Coefficients of variation; MHBMA = Monohydroxybutenyl mercapyuric acid; MR = Mean ratios; S-PMA = S-phenylmercapturic acid; Total NNAL = Total 4-(methylnitrosamino)-1-(3-pyridyl)-1-butanol; CHTP 1.2 = Carbon Heated Tobacco Product 1.2.

This sample size is needed to attain 80% power to detect a 50% reduction or more in the levels of MHBMA, 3-HPMA, S-PMA, and COHb in the CHTP 1.2 arm compared to the CC arm after 5 days of exposure, and in the levels of total NNAL in the CHTP 1.2 arm compared to the CC arm after 90 days of exposure, using a one sided test with 2.5% type I error probability. The overall type I error will be protected by using a closed testing procedure (i.e., testing the four above listed endpoints simultaneously)

Confidentiality Statement

Data and information contained in this document are considered to constitute trade secrets and confidential commercial information, and the legal protections provided to such trade secrets and confidential information are hereby claimed under the provisions of applicable law. No part of this document may be publicly disclosed without the written consent of Philip Morris Products S.A.

TABLE OF CONTENTS

SYNOPSIS.....	8
TABLE OF CONTENTS.....	21
LIST OF ABBREVIATIONS AND DEFINITIONS OF TERMS	26
1 ETHICS AND REGULATIONS	32
1.1 Independent Ethics Committee (IEC) Approval.....	32
1.2 Ethical Conduct of the Study	33
1.3 Subject Information and Consent	33
1.4 Good Clinical Practice and Regulatory Requirements.....	34
2 INTRODUCTION	36
2.1 Background	36
2.2 Purpose of the Study.....	37
2.3 Anticipated Benefits and Risks.....	37
3 STUDY OBJECTIVES	39
3.1 Primary Objectives and Endpoints	39
3.2 Secondary Objectives and Endpoints	39
3.3 Exploratory Objectives and Endpoints.....	43
4 INVESTIGATIONAL PLAN	45
4.1 Overall Study Design and Plan.....	45
4.2 Rationale for Study Design	49
4.3 Appropriateness of Measurements	52
4.4 Study Duration	53
5 STUDY POPULATION.....	54
5.1 Inclusion Criteria	54
5.2 Exclusion Criteria	55
5.3 Discontinuation of Subjects from the Study	57
5.4 Lost to Follow-up	59

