12.1.5 Significance Level for Inferential Analysis

Unless stated otherwise, all statistical tests will be conducted using a one-sided test with 2.5% type I error probability, and all quoted confidence intervals (CIs) will be two-sided 95% CIs.

The primary endpoints will be tested using a multiple testing procedure to preserve the overall alpha level by simultaneously testing the endpoints using a closed procedure with each test performed at the one-sided 2.5% type I error probability. This implies that statistical significance is required for all primary endpoints in order to be able to make confirmatory claims about any of the endpoints.

Full details of this approach will be provided in the SAP.

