12.2 Determination of Sample Size and Power Consideration

The following discussion addresses the ability to detect a reduction of 50% or more in the levels of MHBMA, 3-HPMA, S-PMA, and COHb on Day 5 and in total NNAL after 90 days in smokers switching from CC to the CHTP 1.2 as compared to smokers continuing to use CC, using a one-sided test with 2.5% type I error probability.

[Table 20](#) describes the expected coefficients of variation (CV) and mean ratios (MR) between CHTP 1.2 and the one control arm based on data from a controlled, randomized, open-label, 3-arm parallel single-center confinement study that investigated exposure to selected smoke constituents in smokers switching from CC to smoking article cigarettes for 5 days, the YVD-CS01-EU study (ClinicalTrials.gov ID: NCT00812279) sponsored by PMI.

Confidentiality Statement

Data and information contained in this document are considered to constitute trade secrets and confidential commercial information, and the legal protections provided to such trade secrets and confidential information are hereby claimed under the provisions of applicable law. No part of this document may be publicly disclosed without the written consent of Philip Morris Products S.A.

Table 20 Expected Mean Ratios and Coefficients of Variation for CHTP 1.2/CC after 5 Days of exposure

	CHTP 1.2/CC MR (CV)
COHb	0.40 (0.32)
3-HPMA	0.30 (0.50)
MHBMA	0.15 (0.70)
S-PMA	0.20 (0.70)

Abbreviations: 3-HPMA = 3-hydroxypropylmercapturic acid; CC = Combustible cigarettes; COHb = Carboxyhemoglobin; CV = Coefficients of variation; MHBMA = Monohydroxybutenyl mercaptyuric acid; MR = Mean ratios; S-PMA = S-phenylmercapturic acid; CHTP 1.2 = Carbon Heated Tobacco Product 1.2.

Table 21 describes the expected coefficients of variation (CV) and mean ratios (MR) in total NNAL after 90 days between CHTP 1.2 and the one control arm based on a randomized, controlled, forced-switching, open-label, parallel-group, single-center study in 90 male and female adult smokers to evaluate six biomarkers of tobacco smoke exposure over a 12-week period of unrestricted smoking in the participants' normal life setting [48].

Table 21 Expected Mean Ratios and Coefficients of Variation for CHTP 1.2/CC after 90 Days of exposure

	CHTP 1.2/CC MR (CV)
Total NNAL	0.30 (0.60)

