Abbreviations: Total NNAL = Total 4-(methylnitrosamino)-1-(3-pyridyl)-1-butanol; MR = Mean ratio; CHTP 1.2 = Carbon Heated Tobacco Product 1.2; CC = Combustible cigarettes; CV = Coefficient of variation.

The power to detect a reduction was computed.

Table 22 describes the expected power to detect a reduction of 50% or more in the levels of MHBMA, 3-HPMA, S-PMA, and COHb in CHTP 1.2 arm compared to the CC arm after 5 days of exposure and total NNAL after 90 days of exposure, with a one sided test with 2.5% type I error probability using the assumptions from YVD-CS01-EU and, and 120 randomized subjects in a 2:1 ratio (80 in CHTP 1.2 arm and 40 in CC arm). It is assumed that a minimal number of subjects will be excluded from the PP set in confinement for both arms and CC in ambulatory, whereas at least 50% will remain in the PP set in ambulatory for CHTP 1.2, therefore a 2:1 randomization ratio was chosen.

Confidentiality Statement

Data and information contained in this document are considered to constitute trade secrets and confidential commercial information, and the legal protections provided to such trade secrets and confidential information are hereby claimed under the provisions of applicable law. No part of this document may be publicly disclosed without the written consent of Philip Morris Products S.A.

Table 22 Expected Power

Assumptions	Reduction					
	50%	51%	52%	53%	54%	55%
YVD-CS01-EU	94%	88%	81%	70%	56%	38%

The test-wise powers to detect a reduction of 50% or more in the levels of MHBMA, 3-HPMA, S-PMA, and COHb on Day 5 and in total NNAL after 90 days in smokers switching from CC to the CHTP 1.2 as compared to smokers continuing to use CC, using a one-sided test with 2.5% type I error probability using the assumptions from YVD-CS01-EU, and 120 randomized subjects in a 2:1 ratio (80 in CHTP 1.2 arm and 40 in CC arm) are described in [Table 23](#).

Table 23 Test-Wise Power

Parameter	Test-Wise Power
COHb	96%
3-HPMA	>99%
MHBMA	>99%
S-PMA	>99%
Total NNAL	98%

Given the above calculation, the sample size was considered sufficient to have more than 80% power to detect a reduction of 50% or more in the levels of MHBMA, 3-HPMA, S-PMA, and COHb in CHTP 1.2 arm compared to the CC arm after 5 days of exposure, and in the levels of total NNAL in the CHTP 1.2 arm compared to the CC arm after 90 days of exposure, using a one sided test with 2.5% type I error probability.

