**Table 9 Expected Mean Ratios and Coefficients of Variation for CHTP 1.2/CC after 90 Days of exposure**

	CHTP 1.2/CC MR (CV)
Total NNAL	0.30 (0.60)

Abbreviations: Total NNAL = Total 4-(methylnitrosamino)-1-(3-pyridyl)-1-butanol; MR = Mean ratio; CHTP 1.2 = Carbon Heated Tobacco Product 1.2; CC = Combustible cigarettes; CV = Coefficient of variation.

The power to detect a reduction was computed and is presented below.

Table 10 describes the expected power to detect a reduction of 50% or more in the levels of MHBMA, 3-HPMA, S-PMA, and COHb in CHTP 1.2 arm compared to the CC arm after 5 days of exposure and total NNAL after 90 days of exposure, with a one sided test with 2.5% type I error probability using the assumptions from YVD-CS01-EU and, and 120 randomized subjects in a 2:1 ratio (80 in CHTP 1.2 arm and 40 in CC arm). It is assumed that a minimal number of subjects will be excluded from the PP set in confinement for both arms and CC in ambulatory, whereas at least 50% will remain in the PP set in ambulatory for CHTP 1.2, therefore a 2:1 randomization ratio was chosen.

Table 10 Expected Power

Assumptions	Reduction					
	50%	51%	52%	53%	54%	55%
YVD-CS01-EU	94%	88%	81%	70%	56%	38%

The test-wise powers to detect a reduction of 50% or more in the levels of MHBMA, 3-HPMA, S-PMA, and COHb on Day 5 and in total NNAL after 90 days in smokers switching from CC to the CHTP 1.2 as compared to smokers continuing to use CC, using a one-sided test with 2.5% type I error probability using the assumptions from YVD-CS01-EU, and 120 randomized subjects in a 2:1 ratio (80 in CHTP 1.2 arm and 40 in CC arm) are described in **Table 11**.

Table 11 Test-Wise Power

Parameter	Test-Wise Power
COHb	96%
3-HPMA	>99%
MHBMA	>99%
S-PMA	>99%

Total NNAL 98%

Given the above calculation, the sample size was considered sufficient to have more than 80% power to detect a reduction of 50% or more in the levels of MHBMA, 3-HPMA, S-PMA, and COHb in CHTP 1.2 arm compared to the CC arm after 5 days of exposure, and in the levels of total NNAL in the CHTP 1.2 arm compared to the CC arm after 90 days of exposure, using a one sided test with 2.5% type I error probability.

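### The synopsis says 120 subjects are needed for 80% power, but the plan's own inputs give about 94% for all five primary endpoints; the table of expected power is an unlabelled lower bound

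*Protocol*

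**What the plan says.** The synopsis, below Table 1, ties 120 subjects to a power figure: "This sample size is needed to attain 80% power to detect a 50% reduction or more" in the five biomarkers.

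Protocol 12.2 describes the same 120 subjects differently. It introduces the calculation with "Table 22 describes the expected power to detect a reduction of 50% or more", prints 94, 88, 81, 70, 56 and 38% for reductions of 50 to 55%, gives test-wise powers in Table 23 (COHb 96%, total NNAL 98%, the other three above 99%), and concludes that "the sample size was considered sufficient to have more than 80% power". SAP section 8 repeats both tables and says "Table 10 describes the expected power to detect a reduction of 50% or more".

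The success rule is in Protocol 12.1.5: "This implies that statistical significance is required for all primary endpoints". SAP 12.1.8 says the same. Neither document says how the test-wise powers were combined or what correlation between endpoints was assumed.

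**The concern.** Because a confirmatory claim needs every primary endpoint, the power that matters is the probability that all five tests succeed. Two printed statements describe it poorly.

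- The synopsis presents 120 as the number required for 80%. Section 12.2 and Table 22 present it as giving more than that. A number needed for 80% and a number that gives 94% are different justifications.
- Table 22 is titled as expected power, but its cells behave like a worst-case combination of the five test-wise powers.

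What is at stake is the stated reason for the sample size in the most-read part of the protocol, and the use of Table 22 to judge how power falls at stricter thresholds. Type I error and the analysis itself are not affected.

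**Working it through.** **Inputs.** Mean ratio (MR) and CV come from Protocol Tables 20 and 21. The test is one-sided at 2.5% (Protocol 12.1.5). Day 5 endpoints have 80 vs 40 evaluable. Total NNAL has 40 vs 40, from the stated minimum of 50% PP retention for CHTP 1.2 in the ambulatory period (Protocol 12.2). The threshold is a ratio of 0.50, taken as printed.

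**Formula.** Two-sample t test on the log scale, with SD = √ln(1+CV²), effect = ln(0.50/MR), SE = SD·√(1/n₁+1/n₂), and power from the noncentral t distribution with noncentrality effect/SE.

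| Endpoint | SD | Effect | SE | Noncentrality | Power | Table 23 |
|---|---|---|---|---|---|---|
| COHb | 0.312 | 0.223 | 0.0605 | 3.69 | 95.55% | 96% |
| 3-HPMA | 0.472 | 0.511 | 0.0915 | 5.58 | 99.98% | >99% |
| MHBMA | 0.631 | 1.204 | 0.122 | 9.85 | about 100% | >99% |
| S-PMA | 0.631 | 0.916 | 0.122 | 7.49 | about 100% | >99% |
| Total NNAL | 0.555 | 0.511 | 0.124 | 4.12 | 98.25% | 98% |

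Table 23 is reproduced, so the model is consistent with the plan's.

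**Joint power at 120.** The correlation is not given, so three rules span the range from worst to best case:

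- Boole bound (sum minus 400%): 93.8%
- independence (product): 93.9%
- perfect positive dependence (minimum): 95.5%

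None is near 80%. The synopsis refers to four endpoints in its closed-testing sentence; the four Day 5 endpoints alone give 95.5% under independence, so that reading does not lead to 80% either.

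**Number needed for 80%**, with 2:1 randomisation:

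| CHTP 1.2 retention at Day 90 | Independence | Boole bound |
|---|---|---|
| 50% | 87 subjects (81.2%); 84 gives 79.3% | 87 subjects (80.3%); 84 gives 78.1% |
| 100% | 78 subjects (80.2%) | 81 subjects (81.6%) |

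With 50% retention, a further PP loss of 5% in both arms raises the independence figure from 87 to 90, and a loss of 10% raises it to 96.

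**Table 22.** The same calculation at each threshold, rounding each test-wise power to a whole percent before summing (MHBMA and S-PMA are 100 throughout):

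| Reduction | COHb + 3-HPMA + NNAL, rounded | Sum of five − 400 | Printed | Boole, unrounded | Independence | Perfect dependence |
|---|---|---|---|---|---|---|
| 50% | 96+100+98 | 94 | 94 | 93.8 | 93.9 | 95.5 |
| 51% | 91+100+97 | 88 | 88 | 88.8 | 89.1 | 91.5 |
| 52% | 85+100+96 | 81 | 81 | 81.1 | 81.6 | 84.9 |
| 53% | 75+100+95 | 70 | 70 | 69.9 | 71.2 | 75.3 |
| 54% | 63+100+93 | 56 | 56 | 55.2 | 58.1 | 63.0 |
| 55% | 49+99+90 | 38 | 38 | 37.9 | 43.6 | 48.9 |

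All six printed cells match the rounded sum. Independence, rounded to whole percent, matches only the first. Because of the rounding, the row is not quite a clean bound: 88 lies below the unrounded minimum of 88.8, and 56 lies above 55.2.

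**The case against.** A fair defence runs as follows. The body of the protocol and the SAP already say more than 80% and print 94%, so the synopsis is one loose sentence that errs on the safe side. A bound that holds under any correlation is a legitimate planning choice when correlations are unknown. The use of that bound is inferred, since no document states the method. Nor is 120 arbitrary: at the 52% threshold it is the smallest 2:1 total that reaches 80% by the bound (81.1%, against 79.7% at 117), although the documents do not give this as the basis.

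Most of this stands, and it limits the point. The choice of a bound is not an error; what is missing is a label saying that it is one. The defence does not rescue the synopsis sentence, which names the 50% reduction and 80% together.

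A reader might infer more, and the documents do not support it:

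- *That the stated joint power does not fit the all-five rule.* The 94% cell does fit it, under every dependence assumption tried.
- *That Table 22 is 6 to 11 points too low.* That gap is in the 55% column only, 6 points under independence and 11 under perfect dependence. At 50%, the design criterion, it is at most about 1.5 points.
- *That 33 subjects were surplus.* The difference 120 − 87 holds only with no other PP loss, and it ignores the margin that Table 22 shows at stricter thresholds.

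**Conclusion.** The synopsis misstates the sample-size justification: 120 subjects give about 94% (93.8 to 95.5%) joint power at the 50% threshold, not 80%. Roughly 78 to 87 subjects would give 80%, for ambulatory PP retention between 100% and 50%, with no other PP loss and without relying on positive dependence between endpoints. Table 22 and SAP Table 10 carry an unlabelled, rounded lower bound under the title of expected power. It is essentially right at 50% and increasingly cautious beyond that, reaching 38% against 44 to 49% at 55%.

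Both faults understate power. A reader might take them as a sign of an underpowered trial; the figures show the opposite. These results rest on the planning ratios and CVs and on the 50% threshold as printed. The confirmatory null in Protocol 12.4.4 and SAP 12.5.1.2 is a ratio of 1, for which every test-wise power is about 100%. That is a separate matter, but it means any power statement has to name its threshold.

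**What to change.** 1. **Synopsis, below Table 1.** Align the sentence with section 12.2, for example: *120 randomised subjects give about 94% power to show a reduction of more than 50% (ratio threshold 0.50) on all five primary endpoints jointly, assuming 80 vs 40 evaluable on Day 5 and 40 vs 40 in the PP set at Day 90.* The 78 to 87 range need not be added, since it depends on PP losses.
2. **Protocol Table 22 and SAP Table 10.** Retitle as *Minimum joint power (lower bound, any correlation)* and compute the row from unrounded test-wise powers: 94, 89, 81, 70, 55 and 38%. State in 12.2 and SAP section 8 how the five powers were combined and which evaluable numbers were used. Substituting the independence row is less attractive, because it adds an assumption that the documents do not support for biomarkers measured in the same smokers.

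The cost is one sentence, one table title and two changed cells (51% and 54%) in each document's table, plus a line on method. Enrolment, data and analysis stay as they are.

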Table A1	Study Assessments (Separate Table [Table A2] Shown for 24-hour Urine Collections)	150
Table A2	Schedule for 24-hour Urine Collection Assessments.....	157

LIST OF IN-TEXT FIGURES

Figure 1	Study Design.....	15
Figure 2	Study Design.....	45

Confidentiality Statement

Data and information contained in this document are considered to constitute trade secrets and confidential commercial information, and the legal protections provided to such trade secrets and confidential information are hereby claimed under the provisions of applicable law. No part of this document may be publicly disclosed without the written consent of Philip Morris Products S.A.

LIST OF APPENDICES

Appendix A	Schedule of Events.....	150
Appendix B	Participating Laboratories.....	158
Appendix C	Prochaska “Stage of Change” Questionnaire	159
Appendix D	Summary of Biomarkers of Exposure to HPHC	161
Appendix E	Abnormal Laboratory Values	163

Confidentiality Statement

Data and information contained in this document are considered to constitute trade secrets and confidential commercial information, and the legal protections provided to such trade secrets and confidential information are hereby claimed under the provisions of applicable law. No part of this document may be publicly disclosed without the written consent of Philip Morris Products S.A.

LIST OF ABBREVIATIONS AND DEFINITIONS OF TERMS

Abbreviations

1-NA	1-aminonaphthalene
2-NA	2-aminonaphthalene
3-HMPMA	3-hydroxy-1-methylpropyl-mercapturic acid
3-HPMA	3-hydroxypropylmercapturic acid
4-ABP	4-aminobiphenyl
4-HNE	4-hydroxy-2-nonenal
8-epi-PGF2 α	8-epi-prostaglandin F2 α
8-OHdG	8-hydroxy-2'-deoxyguanosine
11-DTX-B2	11-dehydro-thromboxane B2
ADL	Activities of daily living
AE	Adverse event
ANOVA	Analysis of variance
Apo A1	Apolipoprotein A1
Apo B	Apolipoprotein B
ATS	American Thoracic Society
BMI	Body mass index
BoExp	Biomarker of exposure
CAF	Caffeine
CC	Combustible cigarette(s)
CD	Compact disc
CEMA	2-cyanoethylmercapturic acid
CI	Confidence interval
CHTP	Carbon Heated Tobacco Product
CO	Carbon monoxide
COHb	Carboxyhemoglobin
COPD	Chronic obstructive pulmonary disease
CRF	Case report form

Confidentiality Statement

Data and information contained in this document are considered to constitute trade secrets and confidential commercial information, and the legal protections provided to such trade secrets and confidential information are hereby claimed under the provisions of applicable law. No part of this document may be publicly disclosed without the written consent of Philip Morris Products S.A.

CRO	Contract research organization
CSR	Clinical study report
CTCAE	Common Terminology Criteria for Adverse Events and Common Toxicity Criteria
CTMS	Clinical trial management system
CV (documentation)	Curriculum vitae
CV (statistics)	Coefficient of variation
CVD	Cardiovascular diseases
CYP1A2	Cytochrome P450 1A2
CYP2A6	Cytochrome P450 2A6
DMP	Data management plan
DNA	Deoxyribonucleic acid
ECG	Electrocardiogram
ENDs	Electronic nicotine devices
EOS	End of study
ERS	European Respiratory Society
FAS	Full analysis set
FDA	Food and Drug Administration
FEF	Forced expiratory flow
FEV ₁	Forced expiratory volume in 1 second
FTND	Fagerström Test for Nicotine Dependence (revised version)
FVC	Forced vital capacity
GCP	Good Clinical Practice
HbA1c	Hemoglobin A1c
HDL	High density lipoprotein
HEMA	2-hydroxyethylmercapturic acid
HIV	Human immunodeficiency virus
HMPMA	3-hydroxy-1-methylpropyl-mercapturic acid
HPhCs	Harmful and potentially harmful constituents

Confidentiality Statement

Data and information contained in this document are considered to constitute trade secrets and confidential commercial information, and the legal protections provided to such trade secrets and confidential information are hereby claimed under the provisions of applicable law. No part of this document may be publicly disclosed without the written consent of Philip Morris Products S.A.

hs-CRP	High sensitive C-reactive protein
IB	Investigator's brochure
ICF	Informed consent form
ICH	International Conference on Harmonization
IEC	International Ethic Committee
IP	Investigational product
IRB	Institutional Review Board
ISO	International Organization for Standardization
ITUQ	Intent to Use Questionnaire
IU	International unit
IV	Intravenous
IxRS	Interactive web/voice response system
LDL	Low density lipoprotein
LLN	Lower limit of the normal range
LLOQ	Lower limit of quantification
LPO	Lipid peroxidation
MCEQ	Modified Cigarette Evaluation Questionnaire
MedDRA	Medical Dictionary for Regulatory Activities
MHBMA	Monohydroxybutenylmercapturic acid
MPO	Myeloperoxidase
MR	Mean ratio
MRTTP	Modified risk tobacco product
n	Number of subjects
NEQ	Nicotine equivalents: molar sum of free nicotine, nicotine-glucuronide, free cotinine, cotinine-glucuronide, free trans -3'-hydroxycotinine, trans -3'-hydroxycotinine-glucuronide
NNK	4-(methylnitrosamino)-1-(3-pyridyl)-1butanone
NRT	Nicotine replacement therapy
NSAID	Nonsteroidal anti-inflammatory drugs
o-tol	o-toluidine

Confidentiality Statement

Data and information contained in this document are considered to constitute trade secrets and confidential commercial information, and the legal protections provided to such trade secrets and confidential information are hereby claimed under the provisions of applicable law. No part of this document may be publicly disclosed without the written consent of Philip Morris Products S.A.

PGF2 α	Prostaglandin F2 α
PGHSs	Prostaglandin-endoperoxide synthases
PI	Principal Investigator
PMI	Philip Morris International
PP	Per protocol
PUFAs	Polyunsaturated fatty acids
PX	Paraxanthine
QC	Quality control
QSU-brief	Questionnaire of Smoking Urges
ROS	Reactive oxygene species
RRP	Reduced risk products
S-PMA	S-phenylmercapturic acid
SA	Smoking abstinence
SAE	Serious adverse event
SAP	Statistical analysis plan
SC	Smoking cessation
SD	Standard deviation
SES	Socio-Economic Status Questionnaire
SHM	Sample handling manual
sICAM-1	Soluble inter-cellular adhesion molecule-1
SMF	Study master file
SMP	Safety management plan
SOP	Standard operating procedure
SRO	Subject reported outcome(s)
T	Time point
T ₀	Time point of first product use during study day
t _{1/2}	Half-life
TAC	Total anti-oxidant capacity
TC	Total cholesterol

Confidentiality Statement

Data and information contained in this document are considered to constitute trade secrets and confidential commercial information, and the legal protections provided to such trade secrets and confidential information are hereby claimed under the provisions of applicable law. No part of this document may be publicly disclosed without the written consent of Philip Morris Products S.A.

TG	Triglycerides
Total 1-OHP	Total 1-hydroxypyrene
Total NNAL	Total 4-(methylnitrosamino)-1-(3-pyridyl)-1-butanol
Total NNN	Total N-nitrosonornicotine
█	█
ULN	Upper limit of the normal range
ULOQ	Upper limit of quantification
VAS	Visual Analogue Scale
vWF	von-Willebrand factor
WBC	White blood cell (count)
WHO	World Health Organization

Confidentiality Statement

Data and information contained in this document are considered to constitute trade secrets and confidential commercial information, and the legal protections provided to such trade secrets and confidential information are hereby claimed under the provisions of applicable law. No part of this document may be publicly disclosed without the written consent of Philip Morris Products S.A.

Explanation of Terms

The following special terms are used in this protocol:

Combustible cigarette (CC)	The term “combustible cigarette” refers to commercially available cigarettes (manufactured) and excludes cigars, pipes, bidis, and other nicotine-containing products.
Carbon Heated Tobacco Product 1.2 (CHTP 1.2)	CHTP 1.2 is a non-menthol tobacco stick which is comparable in shape and form, and is used in a similar manner to a combustible cigarette except that the tobacco contained in the CHTP 1.2 is heated by a Carbon Heat Tip and not burned like in a combustible cigarette..
End of study (EOS)	
The individual end of the study (EOS) for a subject is defined as either the Discharge at Visit 4 or the date of early termination followed by the 28-day Safety Follow-up Period.
 
The EOS of the entire study is the last individual EOS time point during the study.

Randomization	Allocation of the respective product at any time on Day -1 utilizing an interactive web and voice response system (IxRS). On Day 1, the subjects will be individually informed about the product they are randomized to prior to the first product use.
Screening failure	All subjects that are not enrolled are considered as screen failures. Re-screening of subjects who did not meet any entry criteria will not be permitted.

Confidentiality Statement

Data and information contained in this document are considered to constitute trade secrets and confidential commercial information, and the legal protections provided to such trade secrets and confidential information are hereby claimed under the provisions of applicable law. No part of this document may be publicly disclosed without the written consent of Philip Morris Products S.A.

